Protocol Number: ^{18}F -AV-1451-A11

^{18}F -AV-1451 PET Imaging in Professional Fighters

Date and Version:

13 July 2015, Amendment 1

[figure not shown]
Name of Compound:

^{18}F -AV-1451 ([F-18]T807)

Sponsor:

Avid Radiopharmaceuticals
Philadelphia, Pennsylvania USA

Approvals/Signatures and Date:

CONFIDENTIAL

This material is the property of Avid Radiopharmaceuticals (Avid). The information is confidential and is to be used only in connection with matters authorized by Avid and no part of it is to be disclosed to others without prior written permission from Avid.

Sponsor: Avid Radiopharmaceuticals	Name of Compound: ¹⁸ F-AV-1451([F-18]T807)	Active Ingredient(s): 7-(6-[F-18]fluoropyridin-3-yl)-5H-pyrido[4,3-b]indole
Title of Study: ¹⁸ F-AV-1451-A11 “ ¹⁸ F-AV-1451 PET Imaging in Professional Fighters”		
Planned number of subjects (Enrolled): Approximately 30 This study will be divided into the following groups: 
 1. Approximately 15 active professional fighters (boxers and mixed martial artists) who have had at minimum 10 professional fights. 
 a. Approximately 10 with cognitive impairment b. Approximately 5 without cognitive or behavioral complaints 2. Approximately 15 retired professional fighters (boxers and mixed martial artists). 
 a. Approximately 10 with cognitive impairment b. Approximately 5 without cognitive or behavioral complaints Subjects will be recruited from the pool of participants in the Professional Fighters Brain Health Study (PFBHS).		
Name of compound: ¹⁸ F-AV-1451([F-18]T807) Dose: 370 MBq (10 mCi) Route of Administration: Intravenous (IV) bolus		
Study Phase: I		
Study Centers: 1-3 centers in the United States		
Trial Objectives: The primary objectives of this study are: 
 • To explore the use of ¹⁸F-AV-1451 as a biomarker for brain injury related to repetitive head trauma; and • To examine the relationship between clinical presentation and tau deposition as measured by ¹⁸F-AV-1451 uptake in active and retired professional fighters. A secondary objective of this study is: 
 • To expand the ¹⁸F-AV-1451 safety database. 		
Eligibility: Only subjects duly consented and enrolled in the PFBHS protocol (conducted by the Cleveland Clinic with [name] as Principal Investigator) will be considered for participation in this study (see Section 5.3, Selection of Subjects).		

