1. INTRODUCTION

Traumatic brain injury (TBI) is a major public health concern with 1.7 million people in the United States suffering a TBI each year (Faul et al., 2010). There is longstanding evidence linking a history of TBI to increased risk for Alzheimer’s disease (AD) (Graves et al., 1990), and emerging concern that a single TBI could initiate long-term processes leading to dementia that is independent of AD (Johnson et al., 2010). Pathologically, amyloid-beta (A β) deposits have been identified following a single TBI in approximately 30% of patients (Huber et al., 1993; Ikonovic et al., 2004). Plaques found acutely following TBI are typically diffuse, in contrast to the thioflavine-S-positive neuritic plaques characteristic of AD. Thus far, neurofibrillary tangles (NFTs) have not been identified following a single TBI in humans; although the neuropathological evidence is sparse, with the only study examining this issue limited to patients dying within 4 weeks of injury (Smith et al., 2003).

Emerging research suggests that tau pathology similar to that seen in Alzheimer’s disease may be more likely after even a single TBI episode (Johnson et al., 2012). Chronic repetitive TBI has been linked to the pathological entity known as chronic traumatic encephalopathy (CTE). CTE is a clinic-pathological entity characterized post mortem by tau pathology that has been linked to individuals exposed to repetitive, often mild or concussive, head injury such as boxers (Corsellis et al., 1973; Dale et al., 1991; Geddes et al., 1999) and professional football players (McKee et al., 2009; McKee et al., 2013).

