The Professional Fighters Brain Health Study (PFBHS) being conducted at the Cleveland Clinic Lou Ruvo Center for Brain Health is a longitudinal study that focuses on a sample of active and retired professional fighters, and compares them with a control cohort matched for age and level of education. The primary objective of the PFBHS is to determine the relationship between measures of head trauma exposure and other potential modifiers and changes in brain imaging, neurological and behavioral function over time (Bernick, 2013). In this context, the addition of an imaging biomarker that could identify the presence of underlying tau pathology might be useful in understanding the etiology and evolution of CTE, and could potentially identify cases at risk for subsequent neurodegeneration or other clinically important outcomes with implications for management of CTE and/or TBI cases.

¹⁸F-AV-1451 (originally named [F-18]T807 by Siemens Molecular Imaging Biomarker Research group) has been developed as a positron emitting radiopharmaceutical for *in vivo* imaging of tau protein aggregates (Xia et al., 2013). Autoradiography results using tissue sections from human brains showed a strong signal in the grey matter of cortical slices from tau positive brains, but weak or no binding in tau negative, A β positive, or tau and A β negative tissue. Scatchard analysis based on this heterogeneous autoradiography assay yielded an estimated K_d of 15nM. A saturation binding experiment using purified PHF tau isolated from brains of AD patients yielded a K_d value of 0.54 nM.

AV-1451 was assessed in competitive binding assays against a panel of 72 of the most common central nervous system (CNS) targets and no clinically relevant inhibition was seen. AV-1451 was positive in the *in vitro* hERG assay; however, *in vivo* cardiovascular safety pharmacology assessments in dogs showed no evidence of QT prolongation at doses up to 50x the intended maximum human dose (MHD). Nonetheless, until sufficient human cardiovascular safety data are available, initial clinical studies will exclude subjects with a history of risk factors for Torsades de Pointes and subjects taking drugs known to prolong the QT interval.

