10.1.4. Exploratory Analysis

A correlation analysis will be performed to investigate the relationship between flortaucipir SUVR and:

- MMSE
- Beck Depression Inventory II
- Digit span forward/backward
- MRI brain volumes (normalized to intracranial volume)
 - Whole brain volume
 - Gray volume
 - Hippocampal volume
 - Ventricle volume

Contingent on a trending significance in the primary analysis ($p \leq 0.1500$ for contrasts), more correlation analysis will be performed to investigate the relationship between tau deposition as measured by flortaucipir SUVR and:

- Years of fighting
- Age when fighting began
- Number of bouts
- Number of losses
- Number of wins
- Number of draws
- Number of knockouts

A multivariate model may also be derived assuming strong relationships found in the primary and correlation analyses.

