10.1.4.1. Subgroup Analysis

All correlation analysis conducted will be performed for each cognitive group separately, and results will be provided in a table.

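### The fight-exposure correlations pool active and retired fighters without adjusting for status or time since last bout, so they could show a dose relation that is absent within status or hide one that is present

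*SAP*

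**What the plan says.** SAP 10.1.4 makes the exposure correlations conditional on p ≤ 0.15 for the primary contrasts. When that is met, "more correlation analysis will be performed to investigate the relationship between tau deposition as measured by flortaucipir SUVR and" seven fight-history measures. Five are counts (bouts, wins, losses, draws and knockouts), one is the length of the fighting career in years, and one is the age at its start. All seven describe the amount of exposure or the age at which it started. None describes how long ago it ended.

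SAP 10.1.4.1 sets the only split: "All correlation analysis conducted will be performed for each cognitive group separately, and results will be provided in a table". The template in SAP Appendix II, section 1.2, is a plain Pearson PROC CORR with neither a PARTIAL nor a BY statement.

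Fighter status is used elsewhere: in Hypothesis 2 (the two-way ANOVA), in Hypothesis 4 (Fisher's exact test) and in the descriptive summaries by group. The ANOVA model in Appendix II 1.1.2 contains fighter status, cognitive status and their interaction. It has no term for age, exposure or elapsed time.

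The Protocol synopsis plans "Approximately 15 active professional fighters (boxers and mixed martial artists) who have had at minimum 10 professional fights" and "Approximately 15 retired professional fighters (boxers and mixed martial artists"). Each of these groups is to have "Approximately 10 with cognitive impairment" and "Approximately 5 without cognitive or behavioral complaints".

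**The concern.** An active fighter's exposure is still accruing and the time since his last bout is short. A retired fighter's exposure is complete and may have ended years ago. If retired fighters as a group have both more exposure and higher SUVR, a pooled correlation appears even when exposure and SUVR are unrelated among active fighters and among retired fighters. If the two shifts run in opposite directions, a real relation can be cancelled.

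The trigger bears on this. One of the two contrasts that can open these analyses is active versus retired, so they may run because of the group difference that distorts a pooled coefficient.

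Time matters on the Protocol's own account. Its Introduction speaks of "emerging concern that a single TBI could initiate long-term processes leading to dementia that is independent of AD" and says that a tau marker "might be useful in understanding the etiology and evolution of CTE". The first statement concerns a single injury and both are background, so they motivate a look at elapsed time without making it an objective. What is at stake is how the exposure results are read against the first primary objective, the use of flortaucipir as a biomarker of injury from repetitive head trauma.

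**Working it through.** **Inputs from the documents.** Impaired table: 10 active + 10 retired = about 20. Unimpaired table: 5 + 5 = about 10 (Protocol synopsis, SAP 10.1.4.1). Tests are at 0.05 (SAP 10.1.3.1). They are taken as two-sided, as in Hypotheses 1 and 2. SAP 3.2 states that no formal sample size calculation was made, so there is no planned figure to reproduce.

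**Assumed inputs.** The documents give no SUVR or exposure distributions. Let ρ be the correlation within each status group, and let d and g be the retired-minus-active shifts in SUVR and in exposure, in within-group SDs. A range is shown.

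**Step 1: critical values.** |r| = t/√(n−2+t²).
- n=20: 2.101/√(18+4.414) = 0.444
- n=10: 2.306/√(8+5.318) = 0.632

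**Step 2: expected pooled correlation, equal group sizes.** r = (ρ + dg/4)/√[(1+d²/4)(1+g²/4)].

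| ρ | d | g | pooled r |
|---|---|---|---|
| 0 | 0.5 | 0.5 | 0.0625/1.0625 = 0.06 |
| 0 | 1 | 1 | 0.25/1.25 = 0.20 |
| 0 | 1.5 | 1.5 | 0.5625/1.5625 = 0.36 |
| 0.5 | 1 | −1 | (0.5−0.25)/1.25 = 0.20 |
| 0.5 | 1.5 | −1.5 | (0.5−0.5625)/1.5625 = −0.04 |

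**Step 3: rejection rates by simulation** (40,000 runs per case). The adjusted test is the partial correlation given fighter status.

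| n | ρ | d, g | pooled | adjusted |
|---|---|---|---|---|
| 20 | 0 | 0.5, 0.5 | 5.7% | 4.9% |
| 20 | 0 | 1, 1 | 14.1% | 5.2% |
| 20 | 0 | 1.5, 1.5 | 37.7% | 4.8% |
| 10 | 0 | 1, 1 | 8.7% | 5.1% |
| 10 | 0 | 1.5, 1.5 | 19.3% | 5.0% |
| 20 | 0.5 | 1, −1 | 10% | 62% |
| 20 | 0.5 | 1.5, −1.5 | 3% | 61% |

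Hand check of the second row with Fisher's z: z(0.20) = 0.2027, times √17 = 0.836. The chance that a standard normal exceeds 1.96 − 0.836 = 1.124 is about 13%, close to the simulated 14%.

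**Step 4: the trigger.** I approximated it by an active-versus-retired comparison at p ≤ 0.15 in the same subjects, not by the full two-way ANOVA contrast. Given that it is met, the false-positive rate at d=g=1 is 16.8% (n=20) and 12.5% (n=10).

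**Step 5: elapsed time.** As an illustration only, suppose the SUVR signal is proportional to bouts × years since last bout (0 for active, 1 to 30 for retired), with signal SD equal to noise SD. At n=20, the planned correlation with bouts then averages 0.16 and is significant in 11% of runs. Among the 10 retired impaired fighters alone, years since last bout averages r = 0.56 and is significant in 45%. This model is built so that elapsed time matters, and it contains no ageing effect.

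**The case against.** Several counter-arguments have force.

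- **The size is assumed.** Bias needs a shift in both SUVR and exposure, and at 0.5 SD it is negligible (5.7% against 5%). This stands.
- **Threshold.** A reader might set the expected r of 0.36 at 1.5 SD against the n=30 critical value of 0.361 and conclude that group status alone reaches significance. The documents do not support this. SAP 10.1.4.1 reports the correlations by cognitive group, where the critical values are 0.444 and 0.632. The rates in Step 3 are the relevant measure.
- **Active versus retired is analysed.** A reader might infer that the plan leaves this question, or delayed tau build-up, wholly unexamined. It does not: Hypotheses 2 and 4 and a named ANOVA contrast address it, though crudely. Only the exposure correlations lack any view of elapsed time.
- **Status adjustment can overcorrect.** If retired fighters have more uptake because they had more exposure, adjustment removes real dose signal. This stands, and is why the adjusted estimate belongs beside the pooled one and not in its place.
- **Time since last bout is tied to age.** Derived as age at scan minus age at start minus years of fighting, it contains age. In single-scan data an unadjusted correlation could reflect ageing alone. This also stands.
- **The analyses are exploratory and flexible.** SAP 10.1.2 labels all testing exploratory, and SAP 10.1.4 allows a multivariate model. That model is optional, names no covariates and depends on strong relationships having been found, so a masked relation might never lead to it.

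**Conclusion.** The point holds in conditional form. The exposure correlations pool active and retired fighters, adjust for nothing and have no elapsed-time measure, and their trigger includes the active-versus-retired contrast. If the groups differ by about 1 SD or more in both exposure and SUVR, the pooled coefficient can mislead: at n=20, false-positive rates are about 14% at 1 SD and 38% at 1.5 SD, and power for a true within-status correlation of 0.5 is about 10% against 62% when 1 SD shifts are opposed. At 0.5 SD the effect is trivial.

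These figures rest on assumed shifts, normal distributions with equal variances, equal numbers of active and retired fighters, and the planned group sizes being met. The real shifts are unknown. Because the testing is exploratory, the fault affects how a dose relation is interpreted and does not undermine a confirmatory claim. It is still worth correcting, because the change is small and bears on a primary objective.

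**What to change.** **Change to SAP 10.1.4, 10.1.4.1 and the PROC CORR template:**
1. Beside each pooled exposure correlation, report the partial correlation given fighter status (coded 0/1 in a PARTIAL statement), each with a 95% CI.
2. Provide scatter plots of SUVR against each exposure measure, marked by fighter status. Treat any within-status estimates as descriptive.
3. Confirm whether the PFBHS data transferred under Protocol 8.1 hold the date of the last bout. If so, add years since last bout at the flortaucipir scan, among retired fighters, with and without adjustment for age at scan. If not, derive it from age at scan, age at start and years of fighting, but only if the last two are defined on the same basis. The derived value is approximate for careers with gaps.

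**Cost.** SAP wording and a few lines of code, with no new visits or procedures. The last-bout date is not confirmed to be available.

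**Downsides.**
- Estimates are imprecise. A partial correlation of 0.5 at n=20 has z = 0.549 ± 1.96/√16, that is 0.059 to 1.039, or a 95% CI of about 0.06 to 0.78. Within one status group of about 15, the critical |r| is 2.160/√(13+4.666) = 0.51.
- More coefficients appear without multiplicity correction: 7 measures × 2 cognitive groups × 2 SUVR versions = 28 partial correlations beside the 28 pooled ones.
- Status adjustment can remove true dose signal, so both estimates must be shown.
- Years since last bout will remain strongly tied to age, and about 15 retired fighters are unlikely to separate the two.

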10.1.4.1. Subgroup Analysis

All correlation analysis conducted will be performed for each cognitive group separately, and results will be provided in a table.

11. SAFETY AND TOLERABILITY

The safety analysis population will be used for all safety outcomes. There will be no statistical comparisons performed among the safety data.

All safety analysis will be conducted separately for flortaucipir and florbetapir injections.

11.1. Exposure to Study Drugs

Exposure to study medication will be presented for the safety analysis population. All exposure data will be presented in listings by visit to include:

- Injection site (Left Arm, Left Hand, Right Arm, Right Hand, Unknown)
- Net activity administered (MBq)
- Date and time of the Injection
- Saline flush administered (Y/N)

The actual dose (MBq) of flortaucipir and florbetapir received will be summarized by enrolling diagnosis using descriptive statistics (n, mean, SD, median, min, and max) in a table.

11.1.1. Unit Conversion and Volume Calculation

All exposure tables and listings will display volume in MBq. Volume collected in mCi will be converted to MBq as follows:

- $MBq = 37 \times mCi$

11.2. Adverse Events

An AE is any undesirable experience occurring to a subject during a clinical trial, whether or not considered related to the study drug.

Treatment-emergent adverse events (TEAE) are any untoward medical occurrence associated with the use of a drug in humans, whether or not considered drug related. For the purposes of this study, untoward medical occurrences will be considered associated with the use of flortaucipir or florbetapir, and thus be reported as AEs, if they occur within 48 hours after administration of the respective PET tracer. AE that occur after the administration of study drug but outside the 48 hour reporting window will not be reported unless the investigator believes they are attributable to the drug.

The end of study for the purpose of AE reporting is defined as 48 hours after the administration of flortaucipir injection or florbetapir injection (whichever occurs last).

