7.7.2 Adverse Event Definitions

Adverse Events

An adverse event is any undesirable experience occurring to a subject during a clinical trial, whether or not considered related to the study drug.

For reporting purposes, Avid will distinguish among pre-existing conditions, trial-emergent adverse events and treatment-emergent adverse events.

Pre-existing conditions (i.e., undesirable experiences, signs or symptoms that begin prior to the Screening Visit) will be recorded on the medical history eCRF pages. During the study, site personnel will record any change in the condition(s) and occurrence and nature of any AEs. Signs and symptoms that are believed to be due to the pre-existing condition(s) (started prior to dose of study medication) do not have to be recorded in the AEs section of the eCRF, unless there is an increase in frequency and severity.

Trial-emergent adverse events are undesirable experiences, signs or symptoms that begin, or worsen in intensity or frequency, after the informed consent, and prior to administration of the study drug at the imaging visit. Adverse events that occur between the florbetapir F 18 and the ¹⁸F-AV-1451 PET scans outside the 48 hour windows will also be considered trial-emergent adverse events. These will be recorded on the adverse event eCRFs.

Treatment-emergent adverse events are any untoward medical occurrence associated with the use of a drug in humans, whether or not considered drug related. For the purposes of this study, untoward medical occurrences will be considered associated with the use of ^{18}F -AV-1451, and thus be reported as adverse events, if they occur within 48 hours after ^{18}F -AV-1451 administration. Untoward medical occurrences will be considered associated with the use of Florbetapir F 18 Injection, if they occur within 48 hours after Florbetapir F 18 Injection administration.

The end of study, for the purpose of adverse event reporting, is defined as 48 hours after the last study drug administration (^{18}F -AV-1451 or Florbetapir F 18 Injection).

Serious Adverse Event (SAE)

A SAE is an AE that results in one of the following outcomes or constitutes one of the following events:

- Death;
- Initial or prolonged inpatient hospitalization (other than that required by protocol; “social hospitalization” or any hospitalization for non-medical reasons does not constitute a SAE);
- A life-threatening experience (that is, immediate risk of dying);

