7.7.4 Reporting of Serious Adverse Events

Study site personnel must alert Eli Lilly, or its designee, of any SAE within 24 hours of their awareness of the event via a sponsor-approved method. Alerts issued via telephone are to be immediately followed with official notification on study-specific SAE forms.

Serious adverse events occurring after a subject receives a dose of study drug will be collected until 48 hours after the dosing of the study drug, regardless of the investigator’s opinion of causation. Therefore, SAEs that occur later than 48 hours after the dosing of the study drug are not required to be reported unless the investigator feels the events were related to either study drug or a protocol procedure.

If a patient experiences a SAE after signing informed consent, but prior to receiving study drug, the event will NOT be reported unless the investigator feels the event may have been caused by a protocol procedure. Previously planned (prior to signing the ICF) surgeries should not be reported as SAEs unless the underlying medical condition has worsened during the course of the study.

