8. STATISTICAL ANALYSIS

8.1 General Statistical Considerations

All statistical analyses will be performed using SAS® version 8.2 or higher.

The study data collected under PFBHS protocol, such as but not limited to subjects’ demographic and baseline characteristics, history taking, neurological and behavioral evaluations, and MRI will be transferred to Avid for analysis purposes.

Data will be summarized using descriptive statistics (number of subjects [N], mean, standard deviation [SD], median, quartiles, minimum, and maximum) for continuous variables and using frequency count and percentage for discrete variables. The demographic and baseline characteristics data will be summarized for all subjects in the safety population according to clinical group. Safety data will be summarized for all patients.

Subject listings of all data from the eCRFs as well as any derived variables will be presented.

Descriptive Statistics will be applied to describe the ¹⁸F-AV-1451 uptake and florbetapir SUVR distribution by subject enrollment groups (active/retired professional fighters and cognitive impaired/normal). ANOVA test, or comparable non-parametric tests such as the Kruskal-Wallis test when ANOVA’s pre-requisites are not met, will be conducted to detect the differences

in ^{18}F -AV-1451 uptake measurements across the enrollment groups. If an overall difference is detected, then a two sample t-test, or Wilcoxon rank sum test when the pre-requisite of t-test is not met, will be applied to test if there are differences seen in ^{18}F -AV-1451 uptake measurements between pair-wised enrollment groups. Additional exploratory analyses will be applied to explore the relationship among ^{18}F -AV-1451 uptake measurements, cognitive and neurological measurements, and other collected biomarkers in the study subjects.

Additional details concerning statistical analyses will be included in the Statistical Analysis Plan (SAP) to be completed per Avid SOP.

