8.2 Safety Analysis

Vital sign measurements will be summarized by subject(s) and by evaluation time point(s). Changes from baseline (pre-dose time point) values will be determined and summarized.

Adverse events including injection site reactions will be summarized in terms of number and percentage of subjects experiencing an AE. The summary will be further broken down by system organ class (SOC) and preferred term using Medical Dictionary for Regulatory Activities (MedDRA) terms. Adverse events will also be presented by severity, relationship to treatment and seriousness. All subjects who experience SAEs, or who discontinue due to AEs, will be summarized.

Discontinuation

All subjects who discontinued participation prior to completing the study will be listed and their discontinuation reasons will be tabulated.

Vital Signs

Changes in vital signs from baseline will be summarized.

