10.7 Adverse Events

All adverse events encountered during the clinical trial must be documented on the eCRF, whether or not considered drug-related.

Eli Lilly must be notified immediately (as soon as possible, and in all cases within 24 hours) of a drug experience, condition, development, or event, which is considered serious. Eli Lilly must be notified immediately of any findings with the use of the drug that may suggest significant hazards, contraindications, adverse drug reactions (ADRs) and precautions pertinent to the safety of the drug. The investigator will be requested to complete a separate report form in addition to the information on the eCRF. See section 7.7.4 for reporting serious adverse events

If a SAE is determined to be unexpected (not previously reported or described by Avid), and study drug-related, Eli Lilly will notify the investigator in writing. The investigator should forward this notification to the IRB within 24 hours of receipt.

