11.2.1. All AEs

A summary of all AEs will be reported in a listing including:

- SOC
- PT
- Start Date/time

- End Date/time
- Severity
- Relationship to Medication (Y/N)
- Relationship to Study Procedure (Y/N)
- Seriousness (Y/N)
- Lead to Death (Y/N)

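### SAP 11.2's rule for adverse events outside the 48-hour windows conflicts with the protocol, and a procedure-only SAE outside them reaches no SAP adverse event table on either reading

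*SAP*

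**What the plan says.** **SAP.** Section 11.2 defines a TEAE by onset within 48 hours of the respective tracer. It then says: "AE that occur after the administration of study drug but outside the 48 hour reporting window will not be reported unless the investigator believes" the drug to be the cause. Section 11.2.1 nevertheless promises an unrestricted output: "A summary of all AEs will be reported in a listing including" relationship to medication, relationship to procedure, seriousness and death. Every adverse event table that follows (11.2.2 to 11.2.7: overall, severity, the two relationship summaries, serious, leading to death) is confined to TEAEs.

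**Protocol.** Section 7.7.2 says that events between the two scans "outside the 48 hour windows will also be considered trial-emergent adverse events. These will be recorded on the adverse event eCRFs", with no condition on cause. Section 10.7 is as broad: "All adverse events encountered during the clinical trial must be documented on the eCRF, whether or not considered drug-related". Section 8.1 adds: "Subject listings of all data from the eCRFs as well as any derived variables will be presented". For SAEs later than 48 hours after dosing, 7.7.4 lifts the reporting requirement "unless the investigator feels the events were related to either study drug or a protocol procedure". It also keeps an SAE before the first dose reportable if a protocol procedure may have caused it. Section 8.2 sets the output: "All subjects who experience SAEs, or who discontinue due to AEs, will be summarized". It has no 48-hour limit.

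**The concern.** The two documents give different rules for the same events. The SAP's exception names the drug only, whereas protocol 7.7.4 names drug or procedure. The SAP has no trial-emergent category, although the protocol defines one and has its events recorded. The SAP also conflicts with itself, because a listing of all AEs cannot also leave out those that 11.2 says go unreported.

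Expanding the safety database is the study's secondary objective, so the safety outputs are what that objective delivers. The risk is a serious or death table that shows zero although a related SAE was reported to the sponsor, and two programmers building different listings from the same text.

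**Working it through.** The plan gives no figure to reproduce and no event frequency. The check therefore traces each kind of event through both documents, assuming that its onset date is known.

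**Time affected between scans.** Inputs: a 48-hour (2-day) window after each tracer (SAP 11.2, protocol 7.7.2) and scans at most 60 days apart (protocol 5.1, SAP 3.1). For a gap of d days, the share outside the first tracer's window is (d − 2)/d. At d = 60 this is 58/60, about 97%. It is a share of time, not of events, and it applies only to subjects who have both scans.

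**Two readings of the SAP sentence.**
- Reading A: it governs outputs, and a TEAE is strictly an event with onset within 48 hours.
- Reading B: it only qualifies the TEAE definition. A late event attributed to the drug then counts as a TEAE, and the 11.2.1 listing stays complete.

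| Event outside the 48-hour windows | Protocol | A: listing / AE tables | B: listing / AE tables |
|---|---|---|---|
| Between scans, non-serious, drug-related | recorded, listed | yes / no | yes / yes |
| Between scans, non-serious, procedure-only or unrelated | recorded, listed | no / no | yes / no |
| Between scans, serious, unrelated | recorded, listed; 8.2 summary | no / no | yes / no |
| Later than 48 hours, serious, drug-related | reportable; 8.2 summary | yes / no | yes / yes |
| Later than 48 hours, serious, procedure-only | reportable; 8.2 summary | no / no | yes / no |
| Before first dose, serious, procedure-caused | reportable; 8.2 summary | yes / no | yes / no |

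The last row is listed on both readings because the SAP sentence concerns only events after dosing.

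**What depends on the reading.** Omission from the listing occurs only on A. So does the absence of late drug-related SAEs from the tables. The procedure-only SAE is in no adverse event table on either reading, whether it falls after the window or before the first dose.

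**Does the SAP settle which reading applies?** Appendix I 1.2 treats an onset that cannot fall inside the window as not a TEAE and makes no exception for relatedness, which favours A for the tables. But it is written for incomplete dates, so it is not decisive. The 11.2.1 heading and its unrestricted wording favour B for the listing.

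**After the last dose.** Protocol 7.7.2 itself ends adverse event reporting 48 hours after the last tracer. There the conflict is confined to related SAEs kept open by 7.7.4.

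**The case against.** The best defence is that the sentence is a window rule and not an output exclusion. It stands in the 11.2 text that defines TEAEs, and a clause of that form directly after a definition reads naturally as an exception to it. SAP section 1 says that the SAP is to be read together with the protocol, so protocol 8.1 still applies and everything on the eCRF is listed. This stands as far as it goes: omission from the listing is a possible result of the wording, not an established one.

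A second defence is that protocol 8.2 does not call for a table, and that SAP 11.2.1 describes its listing as a summary. With approximately 30 subjects, a listing that shows seriousness, relatedness and death would make any late SAE visible. This also has force, but only if the listing is complete, which is the point left unclear. It also does not stop the serious and death tables from showing zero beside a listed SAE.

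Three stronger inferences are tempting and unsupported:
- That data are lost. The events that the protocol collects stay on the eCRF.
- That late SAEs vanish from every output. Drug-related ones are listed on both readings. One that led to withdrawal could also appear as a reason in the disposition table (SAP 8), though that is not an adverse event table. An event with a missing onset date may be assumed to be a TEAE.
- That SAP 11.2.5 replaces the procedure-relationship table with a second medication table. Two sentences there say medication, but the section heading, its opening sentences and the end of Appendix I make the intent plain. It is a clerical slip.

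Counting the kinds of event affected would not measure the size of the problem either, because it would weigh a minor complaint the same as a related SAE.

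**Conclusion.** The conflict is real and should be corrected. SAP 11.2 is narrower than protocol 7.7.2 and 8.1 on between-scan events and narrower than 7.7.4 on late SAEs, and it contradicts SAP 11.2.1. Two consequences have different strength. Firm on either reading: a procedure-only SAE outside the windows enters no SAP adverse event table. Conditional on the reading: procedure-only and unrelated between-scan events and procedure-only late SAEs are missing from the listing, and drug-related late SAEs are missing from the tables.

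The size in events is unknown. The documents give no event rates and no number of subjects with both scans, and SAEs of this kind may never occur. No efficacy analysis is touched. The conclusion assumes known onset dates and takes protocol 8.2 to intend that SAEs be counted as well as listed.

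**What to change.** Keep the 48-hour TEAE definition and change the SAP as follows.

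1. Replace the sentence on unreported events in 11.2 with a statement that every AE recorded on the eCRF appears in the 11.2.1 listing, flagged as trial-emergent or treatment-emergent per protocol 7.7.2. SAEs after the last window fit neither category, so give them their own flag value.
2. State that a late related event means related to study drug or to a protocol procedure, as in protocol 7.7.4.
3. Add to the serious and death outputs a separate non-TEAE row that counts all subjects with any recorded SAE outside the 48-hour windows, including procedure-caused SAEs before the first dose and SAEs between scans. Show it overall. The relationship fields in 11.2.1 are yes/no and do not name a tracer, so if a split is wanted, use the most recent tracer received; SAEs before the first dose then stay in the overall row only.
4. In 11.2.5, change medication to procedure in the worst-case sentence and the table sentence, as a clerical edit.

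The cost is a little more programming and possibly slightly higher reported SAE counts. No new data collection is needed, since the row counts only what protocol 7.7.2 and 7.7.4 already have recorded or reported.
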